1.2.3.3 Safety Profile

Sunitinib is reasonably well tolerated, with asthenia, hypertension, dermatitis, and mild myelosuppression as the most common AEs.[93] Additionally, the inhibition of TKRs by agents such as sunitinib can result in cutaneous AEs such as acral erythema, subungual splinter hemorrhages, modification of hair and skin pigmentation, mucositis, and (occasionally) periocular edema[94, 95]. Hand-foot skin reaction, a group of signs and symptoms that can affect, usually bilaterally, the hands and/or feet of patients, has occurred in patients receiving sunitinib. A recent analysis of dermatological AEs in patients receiving sunitinib therapy has

reported that all-grade hand-foot skin reactions occurred in 19% of patients (5% grades 3-4), skin discoloration in 28% (no grades 3-4), dry skin in 16% (1% grades 3-4), skin rash in 13% (1% grades 3-4), dermatitis in 8% (2% grades 3-4), hair color changes in 10% (no grades 3-4), alopecia in 6% (no grades 3-4), and phototoxicity in <0.1% (no grades 3-4)[96].

1.2.4 Rationale

The approval, by the FDA, of sunitinib and everolimus for the treatment of unresectable, locally advanced or metastatic NETs is a remarkable milestone in the field of medical therapy of malignant NETs[53-55]. However, there is important management issue that need to be addressed: While the choice of targeted therapies in other malignancies is driven by the findings of the precise molecular alterations present in the tumor, no such study has been done in malignant NETs. This is particularly important given that the survival of patients with malignant NETs appears to be different based on the driver mutation(s) present in the tumor and low- or intermediate grade tumors can have a relatively indolent growth[58].

Surgical resection alone is a valuable treatment option for patients with early-stage disease; however, the extent, timing and effect of surgical intervention for advanced, metastatic NETs remain controversial and difficult to estimate. NETs most commonly metastasize to the loco-regional lymph nodes and liver and 25% to 93% of patients will develop liver metastases throughout the course of their disease[38, 43]. Prospective randomized data on the treatment of liver metastases of NETs are lacking and there is also considerable debate regarding the optimal surgical management[42]. In general, the surgical strategies proposed by different groups can be classified into: 1) resection of the primary tumor and loco-regional metastases (intra-abdominal debulking), 2) resection of isolated liver metastases, or 3) synchronous resection of primary and liver metastases.

Although not supported by randomized clinical trial data, currently it is advocated that surgery should be undertaken only if metastatic disease is confined to the liver and if 90% or more of the tumor mass, including liver metastases, can be successfully removed[47]. However, most patients will present with multiple bilobar liver metastases, and altogether only 5–10% will have apparently solitary or dominant liver metastases amenable to surgical resection[43, 97]. Furthermore, recurrence after surgery is common and a significant number of patients with advanced NETs undergoing debulking surgery will have residual disease and suffer from complications associated with hormonal hypersecretion and or tumor progression[43, 48, 49]. The role of surgical tumor debulking less than the traditionally accepted 90% of tumor mass is currently unknown and it is not clear if adjuvant therapy in this patient population will render favorable outcomes.

Although improving OS is the ultimate goal for any cancer therapy, the variable, and at times long, survival time in many patients with NETs makes OS a less suitable initial end point to study for the proposed strategy of targeted therapy [49, 71]. In this regard, using PFS as a primary end point poses less significant scientific challenges and is attractive from both an ethical and feasibility standpoint[49]. Such an approach will allow us to generate enough data to determine whether a larger study is warranted using genotype targeted therapy.

2 Eligibility assessment and enrollment

2.1 ELIGIBILITY CRITERIA

2.1.1 Inclusion Criteria

- 2.1.1.1 Progressive, histologically or cytologically diagnosed low or intermediate grade, neuroendocrine tumors confirmed by the Laboratory of Pathology, NCI or a pathology laboratory at the enrolling institution. Disease progression is defined according to RECIST criteria for progression of disease (see Section 6.3) or any new lesions seen on 68-Gallium DOTATATE within 18 months prior to enrolment (per PI discretion and if 68-Gallium DOTATATE is performed at the enrolling institution).
- 2.1.1.2 Age \geq 18 years, because the incidence and prevalence of metastatic pancreatic and gastrointestinal neuroendocrine tumors in the pediatric patient population is exceedingly rare (children are excluded from this study, but will be eligible for future pediatric trials).
- 2.1.1.3 Patients must have measurable disease according to RECIST criteria (see Section 6.3) on anatomic imaging studies (CT scan or MRI).
- 2.1.1.4 Willingness to undergo tumor biopsy if the patient does not have a known familial cancer syndrome (MEN1, VHL and NF1) or archival tissue available.
- 2.1.1.5** ECOG performance status <2 (see **Appendices**
- 2.1.1.6 **Appendix A**).
- 2.1.1.7 Patients must have normal organ and bone marrow function as defined below:

- hemoglobin \geq 9 g/dL*
 - leukocytes \geq 3,000/mcL*
 - absolute neutrophil count \geq 1,500/mcL*
 - platelets \geq institutional lower limit of normal*
 - total bilirubin within normal institutional limits
 - AST(SGOT)/ALT(SGPT) \leq 2.5 X institutional upper limit of normal (\leq 5 x ULN in patients with liver metastases)
 - creatinine within normal institutional limits
- OR
- creatinine clearance \geq 60 mL/min/1.73 m² for patients with creatinine levels above institutional normal.
 - INR \leq 2;

*If a patient's bone marrow function falls below the indicated values and it is not thought to be related to prior treatments a hematology consult will be ordered. If Hematology deems the patients safe to proceed with treatment they will be allowed to enroll on study. In such cases, the patient's absolute neutrophil count must be $>$ 1,000/mcL, hemoglobin must be $>$ 7.5 g/dL and the platelet count must be $>$ 75,000 mcL. Each patient will also be seen by a medical oncologist at follow-up visits if possible.

- 2.1.1.8 Fasting serum cholesterol ≤ 300 mg/dL OR ≤ 7.75 mmol/L AND fasting triglycerides ≤ 2.5 x ULN. NOTE: In case one or both of these thresholds are exceeded, the patient can only be included after initiation of appropriate lipid lowering medication;
- 2.1.1.9 Women of childbearing potential (WOCBP) or partners of WOCBP participating in this study must agree to use highly effective contraception while on treatment and for at least 8 weeks after end of treatment, because the effects of sunitinib and everolimus on the developing human fetus are unknown. Should a woman become pregnant or suspect she is pregnant while she or her partner is participating in this study, she should inform her treating physician immediately.

Highly effective contraception methods include combination of:

- a. Any two of the following:
 - Use of oral, injected or implanted hormonal methods of contraception or;
 - Placement of an intrauterine device (IUD) or intrauterine system (IUS);
 - Barrier methods of contraception: condom or occlusive cap (diaphragm or cervical/vault caps) with spermicidal foam/gel/film/cream/ vaginal suppository;
- b. Total abstinence or;
- c. Male/female sterilization.

Women are considered post-menopausal and not of child-bearing potential if they have had 12 months of natural (spontaneous) amenorrhea with an appropriate clinical profile (e.g. age appropriate, history of vasomotor symptoms) or have had surgical bilateral oophorectomy (with or without hysterectomy) or tubal ligation at least six weeks prior to enrollment. In the case of oophorectomy alone, only when the reproductive status of the woman has been confirmed by follow up hormone level assessment is she considered not of child-bearing potential.

- 2.1.1.10 Must have fully recovered from toxicities of any prior treatment with cytotoxic drugs, radiotherapy, surgery, or other anti-cancer modalities (returned to baseline status as noted before most recent treatment or \leq grade 1).
- 2.1.1.11 Ability of subject to understand and the willingness to sign a written informed consent document.

2.1.2 Exclusion Criteria

- 2.1.2.1 Uncontrolled hypertension ($>150/100$ mmHg).
- 2.1.2.2 Prior external beam radiation therapy to the target lesion(s) within 1 months prior to enrollment
- 2.1.2.3 Prior systemic chemotherapy or therapy with one of the investigational agents within 1 month prior to enrollment.
- 2.1.2.4 Patients who had therapy with one of the investigational agents more than 1 month prior to enrollment in whom tumor genotyping show assignment to the same investigational agent.
- 2.1.2.5 Patients who are receiving any other investigational agents.
- 2.1.2.6 Patients with known brain metastases will be excluded from this clinical trial because of their poor prognosis and because they often develop progressive neurologic dysfunction that would confound the evaluation of neurologic and other adverse events.

- 2.1.2.7 History of allergic reactions attributed to compounds of similar chemical or biologic composition to sunitinib or everolimus.
- 2.1.2.8 Patients who have any severe and/or uncontrolled medical conditions such as:
- unstable angina pectoris, symptomatic congestive heart failure, myocardial infarction ≤ 6 months prior to start of everolimus, serious uncontrolled cardiac arrhythmia, or any other clinically significant cardiac disease
 - symptomatic congestive heart failure of New York heart Association Class III or IV
 - active (acute or chronic) or uncontrolled severe infection, liver disease such as cirrhosis, decompensated liver disease
 - known severely impaired lung function
 - QTc interval > 450 msec for males or > 470 msec for females
 - active, bleeding diathesis;
 - psychiatric illness/social situations that would preclude informed consent, limit compliance with study requirements
- 2.1.2.9 Pregnant or nursing patients will be excluded from the study, because the effects of sunitinib and everolimus on the developing human fetus are unknown. Because there is an unknown but potential risk for adverse events in nursing infants secondary to treatment of the mother with sunitinib or everolimus, breastfeeding should be discontinued if the mother is treated with sunitinib or everolimus (**See also Appendix B**).
- 2.1.2.10 Current treatment with therapeutic doses of Coumadin-derivative anticoagulants (low dose Coumadin up to 2 mg PO daily for deep vein thrombosis prophylaxis is allowed).
- 2.1.2.11 HIV-positive patients on combination antiretroviral therapy are ineligible because of the potential for pharmacokinetic interactions with study agents.
- 2.1.2.12 Lack of physical integrity of the upper gastrointestinal tract or malabsorption syndrome, or the inability to take oral medication
- 2.1.2.13 Uncontrolled diabetes mellitus as defined by HbA1c $> 8\%$ despite adequate therapy. Patients with a known history or diagnosis of diabetes mellitus who are on therapy and have had good blood sugar control may be included even if the HbA1c is $> 8\%$ because this value can take up to 3-4 months to normalize;
- 2.1.2.14 Patients who have received live attenuated vaccines within 1 week of start of everolimus and during the study. Patient should also avoid close contact with others who have received live attenuated vaccines. Examples of live attenuated vaccines include intranasal influenza, measles, mumps, rubella, oral polio, BCG, yellow fever, varicella and TY21a typhoid vaccines
- 2.1.2.15 Patients who are on chronic treatment with corticosteroids or other immunosuppressive agents (topical or inhaled corticosteroids are allowed)
- 2.1.2.16 Patients with a history of non-compliance to medical regimens or who are considered potentially unreliable or will not be able to complete the entire study
- 2.1.2.17 Patients who are taking medications that are strong inhibitors of CYP3A4 or PgP and need to remain on these medications. For a current table of Substrates, Inhibitors and Inducers please access the following

website:<http://www.fda.gov/Drugs/DevelopmentApprovalProcess/DevelopmentResources/DrugInteractionsLabeling/ucm093664.htm>

2.1.2.18 Patients who have a history of another primary malignancy from which the patient has been disease free for < 3 years at the time of enrolment, with the exceptions of: a patient with a familial cancer syndrome-associated NETs including MEN1, VHL, NF-1, and TS

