Advanced NETs are characterized by local invasion, and regional and distant metastases. While the treatment of localized NETs is surgical resection, a variety of therapeutic options are available for patients with advanced NETs. These include medical control of excess hormone levels and associated symptoms, cytoreductive surgery for patients with advanced disease, radioembolization, chemoembolization, systemic chemotherapy, interferon, long-acting somatostatin analogs, receptor-targeted radionuclide therapy, and or liver transplantation[33-36]. When to apply a given option, what combination therapeutic approach should be used, how long treatment should be continued, and in what subgroup of patients a particular treatment option should be used is unclear and controversial[37].

[figure not shown]
When feasible, aggressive surgical resection has been associated with the best symptom-free and long-term survival results in patients with advanced NETs[6, 38-46]. Despite the lack of randomized control data, a recent consensus statement from the ENETS emphasized that resection should be the first-line treatment option for patients with advanced NETs if up to 90% of the disease burden is resectable[47]. However, only 5% to 20% of patients with advanced NETs meet this “conventional” criterion[43, 48]. Furthermore, a significant number of patients undergoing debulking surgery will have residual disease and recurrence rates are high[49]. Thus, it is becoming increasingly clear that combination (surgical and medical) therapeutic strategies to improve the outcomes of patients with advanced NETs need to be explored.

Mutation-targeted therapy

Our understanding of the genetic changes associated with sporadic and familial NETs has improved considerably over the last 3 decades. Driver oncogene and tumor suppressor genes have been identified in most NETs[50-56]. Overall, the majority of NETs will have somatic mutations in *MEN1*, the phosphatidylinositol 3-kinase (*PI3K*)/*AKT*/ mammalian target of rapamycin (*mTOR*) signaling pathway[20, 57-61], and or overexpression of growth factors and their receptor such as vascular endothelial growth factor (*VEGF*), *VEGF* receptor (*VEGFR*), platelet-derived growth factor (*PDGF*), and *PDGF* receptor (*PDGFR*) (**Figure 1**)[62-65]. The most common mutations (somatic and germline for familial cancer syndromes) are in *MEN1*,

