2.2 SCREENING EVALUATION

Within 4 weeks prior to enrollment

- Confirmation of progressive, histologically or cytologically diagnosed low or intermediate grade, neuroendocrine tumors locally invasive or metastatic confirmed by the Laboratory of Pathology and the Department of Radiology, NCI or a pathology laboratory and radiology department at the enrolling institution (any time prior to enrollment).
- Brain MRI or CT (if clinically indicated)
- 68-Gallium DOTATATE scan per PI discretion
- Contrast enhanced CT scan or MRI of the chest, abdomen and pelvis (CT C/A/P)
- Bone scan for patients in whom bone metastases are suspected
- FDG PET scan
- HIV antibody
- 24-urine collection and measurement of urinary creatinine, total protein and albumin, and serum creatinine measurement

Within 2 weeks prior to enrollment

- Laboratory Evaluations
 - CBC with differential and platelets
 - Chemistries: Sodium (Na), Potassium (K), Chloride (Cl), Total CO₂ (bicarbonate), Creatinine, Glucose, Urea nitrogen (BUN), Albumin, Calcium total, Alkaline Phosphatase, ALT/GPT, AST/GOT, Total Bilirubin, Total Protein
 - INR
 - Lipid panel (fasting)
 - Hemoglobin A1C
- Complete history and physical examination including height, weight, vital signs and ECOG status
- 12 lead ECG

Within 3 days prior to enrollment

- Serum or urine beta-HCG (in women of childbearing potential)

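### Entry progression need not follow the last anti-tumour therapy, so residual control from an earlier treatment can count toward first-line PFS against the fixed 11 months

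*Combined protocol and SAP*

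**What the plan says.** Time windows for earlier therapy stand in section 2.1.2. Item 2.1.2.3 excludes "Prior systemic chemotherapy or therapy with one of the investigational agents within 1 month prior to enrollment", and item 2.1.2.2 excludes "Prior external beam radiation therapy to the target lesion(s) within 1 months prior to enrollment". Item 2.1.2.5 bars "Patients who are receiving any other investigational agents", which concerns current use only.

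For all other modalities, item 2.1.1.10 sets a toxicity condition with no interval: "Must have fully recovered from toxicities of any prior treatment with cytotoxic drugs, radiotherapy, surgery, or other anti-cancer modalities". Section 1.2.1 names further options for advanced NETs: two forms of embolization, interferon, and a list ending "long-acting somatostatin analogs, receptor-targeted radionuclide therapy, and or liver transplantation".

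On progression, item 2.1.1.1 says "Disease progression is defined according to RECIST criteria for progression of disease", or alternatively new lesions on DOTATATE imaging with an 18-month look-back. Section 2.2 asks for confirmation of progressive disease by pathology and a "radiology department at the enrolling institution (any time prior to enrollment").

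Section 6.3.6 starts the PFS clock at the start of each treatment. Section 8 tests each arm's median PFS against a published 11 months, with no concurrent control. It plans no analysis by prior or recent therapy.

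**The concern.** A single-arm comparison with a fixed median attributes all disease control after day 1 to the study drug. That is fair only if patients enter with disease that is growing despite whatever they last received. The usual safeguard is to require progression on or after the most recent therapy, and this plan has no such requirement.

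A patient could progress, receive radionuclide therapy or embolization, respond to it, recover from its toxicity, and still qualify on the earlier progression. Continued control from that therapy would lengthen first-line PFS, and in the primary analysis it would look the same as a benefit of genotype-matched treatment. Section 8 says that a favourable PFS finding would lead to a larger randomized trial, so the decision at stake is whether to launch that trial.

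**Working it through.** **Eligibility text, side by side**

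| Prior therapy | Time window | Progression required afterwards? |
|---|---|---|
| Systemic chemotherapy | 1 month (2.1.2.3) | No |
| Sunitinib or everolimus | 1 month (2.1.2.3); excluded at any interval if genotyping assigns the same drug (2.1.2.4) | No |
| External beam radiation to target lesions | 1 month (2.1.2.2) | No |
| Other investigational agents | Current use only (2.1.2.5) | No |
| Embolization, radionuclide therapy, interferon | None; toxicity recovery (2.1.1.10) and organ function (2.1.1.7) | No |

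The 18 months in 2.1.1.1 may apply to DOTATATE alone or to both routes. If to DOTATATE alone, RECIST progression has no look-back limit. Under either reading the progression can predate the last therapy.

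**Reproducing the plan's power.** Inputs from section 8: n = 44 per arm, null median 11 months, alternative 18 months, one-sided alpha 0.10, 12 months of follow-up after accrual. With that follow-up there is no administrative censoring before month 11, so the Brookmeyer-Crowley test reduces to testing S(11) against 0.50.

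- Under exponential PFS with median 18, S(11) = 2^(-11/18) = 0.655.
- Null standard error = sqrt(0.25/44) = 0.0754. The critical value is 0.50 + 1.2816 × 0.0754 = 0.597.
- Power = Φ[(0.655 − 0.597)/sqrt(0.655 × 0.345/44)] = 79.1%. With the alternative variance throughout it is 81.0%.

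The stated 80% is reproduced, so the sample size is not in question.

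**Illustration of carry-over.** Two inputs are assumptions that the documents do not give: the share f of an arm with carry-over, and the delay d in months. Let the study drug do no better than a median of 11 months. Then

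S(11) = (1 − f) × 0.5 + f × 2^(−(11 − d)/11),

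where 2^(−8/11) = 0.604 for d = 3 and 2^(−5/11) = 0.730 for d = 6. The chance of declaring the arm better than 11 months is Φ[(S(11) − 0.597)/sqrt(S(11)(1 − S(11))/44)].

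| f | d | S(11) | Normal approximation | Simulation |
|---|---|---|---|---|
| 0 | – | 0.500 | 0.10 | 0.088 |
| 10% | 3 | 0.510 | 0.13 | 0.109 |
| 10% | 6 | 0.523 | 0.16 | 0.149 |
| 20% | 3 | 0.521 | 0.16 | 0.139 |
| 20% | 6 | 0.546 | 0.25 | 0.224 |
| 30% | 3 | 0.531 | 0.19 | 0.173 |
| 30% | 6 | 0.569 | 0.36 | 0.333 |

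The simulation uses Kaplan-Meier estimates with Greenwood variance and uniform accrual over 48 months. It starts from 0.088 rather than 0.10 because the test is discrete at n = 44.

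**The case against.** **Partial filters exist.** Patients must have progressive disease, toxicity from earlier treatment must be back to baseline or grade 1 or less, and 2.1.1.7 limits blood counts, bilirubin and transaminases. Its marrow exception is closed to low counts thought to come from prior treatment. A reader might infer that patients treated days before enrollment will commonly enter. The text does not exclude such a patient, but these criteria make the case less likely. They do not test for residual anti-tumour effect.

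**A new baseline is taken.** Imaging is repeated before treatment, and progression is measured from the smallest sum on study. Shrinkage before baseline therefore earns no PFS time by itself, and later shrinkage lowers the reference. Continued control after baseline is still credited.

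**The section 2.2 wording may be meant for histology.** It sits under a 4-week heading, and the study calendar in section 3.4 names only histopathological confirmation. That is plausible, but as written it also covers radiology, and correcting it alone would not link progression to the last therapy.

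**Recent therapy is partly recorded.** Section 4.2.1 captures drugs and significant non-drug therapies from 28 days before study treatment, and a complete history is taken at screening. Very recent treatment is therefore not invisible. Therapy given six weeks earlier falls outside the 28-day rule, and no analysis uses either source.

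**Frequency and net bias are unknown.** Section 1.2.1 lists available options. A reader might infer that enrolled patients had received them recently, but the documents do not say so. The benchmark trials' rules on prior therapy are not given either. If those trials had the same carry-over, the 11 months would already contain it. This stands and limits the claim to a possible bias.

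**The result is exploratory.** Section 8 describes preliminary data leading to a randomized trial. That lowers the stakes but does not remove the reason for a cheap safeguard.

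**Conclusion.** The gap holds as a matter of text: no section requires the qualifying progression to follow the most recent anti-tumour therapy. The plan as written can therefore credit another treatment's effect to first-line PFS.

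The size is not established. The range of about 0.13-0.36 (0.11-0.33 by simulation) against a nominal 0.10 rests on assumed shares of 10-30%, assumed delays of 3-6 months, exponential PFS, and a benchmark free of the same effect. A share near zero is equally compatible with the documents, so the range is not an estimate of this trial's error rate.

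A reader might also infer that extending the 1-month wash-out to every modality would settle the matter. The documents support no particular interval for those modalities, and a 1-month window would leave most of a 3-6 month delay in place. Requiring progression after the last therapy is the element that addresses the bias.

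**What to change.** 1. In 2.1.1.1 and 2.2, require the qualifying progression to be documented on imaging done after the last anti-tumour therapy, with background octreotide permitted as in section 4.1. Limit the any-time allowance in 2.2 to histology.
2. Record the type and date of the last anti-tumour therapy for all patients, including those already enrolled, because the rule in 4.2.1 reaches back only 28 days.
3. Add to section 8 a per-arm PFS sensitivity analysis that excludes patients without documented progression after their last therapy.

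Whether other modalities also need a wash-out, and how long, is for the investigators to set.

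The cost is a short eligibility amendment, a little more data collection, and a few patients delayed or not enrolled. The planned sample size does not change. Items 2 and 3 need no eligibility change and remain useful even if accrual is well advanced.
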